10.0 Efficacy Analysis

10.1 General Considerations

When the last patient completes the Week 28 visit, the Primary Analysis will be performed including all efficacy endpoints pertaining to Part A. This is the only and final analysis for these endpoints, hence no alpha adjustment is required. For this primary analysis, all endpoints will be analysed up to Week 28, with the following exception:

- Categorical endpoints related to PASI and sPGA, using the LOCF method, will be analysed up to the last visit that at least one subject has observed PASI and sPGA measurements, respectively.

The treatment effect will be evaluated based on a two-sided significance level of 0.05 (when rounded to three decimal places).

The ITT population will be used for the analyses of efficacy endpoints. The following treatment periods will be analyzed:

- Part A (up to Week 16)
- Part B (Week 16 and after)

Time-to-event analysis will be performed across the entire study for subjects who are randomized to risankizumab or placebo arms in addition to the analyses in Part A.

Primary variable will also be analyzed for the per-protocol populations using primary approach to handle missing data as described in Section [10.1.4](#).

Subjects' actual Concomitant PsA at baseline (Yes: Diagnosed or Suspected; versus: No) and body weight (≤ 90 kg versus > 90 kg) will be used as the strata in the stratified analyses.

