4.4 Interim Analysis

Before the submission to regulatory agencies with the long-term data, an interim report will be prepared for the submissions analysis pertaining to Part A. Primary endpoint (PASI 90 score at Week 16) for all patients will be included in the Week 28 analyses, which is the only and final analysis for the primary endpoint; hence no alpha adjustment is required. For this analysis all efficacy endpoints and safety as well as PK and immunogenicity data will be analysed. As endpoints for Week 28, same analyses will be performed for the Week 52 endpoints defined in Section 10.3.

AbbVie Data and Statistical Sciences will be unblinded to perform this analysis. Unblinded treatment assignments will not be disseminated to BI, the sites, investigators, or patients until the end of final database lock.

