Table 4.
Visit Windows for Analysis of ECG in Part A (Safety Population)

Window Label	Target Day	Interval
Baseline	1	≤ 1
Week 4	29	[2, 71]
Week 16	113	[72, 155*]

Rx Day calculated relative to first dose date of study drug.

* The minimum of upper bound, the first dose date in Part B, and the last dose + 105 days.

Table 5. Visit Windows for Analysis of sPGA, PSS, DLQI, HAQ-DI, Pain VAS, Investigator's Global Assessment VAS, Patient's Global Assessment VAS, CRP as an ACR 20 Component, SJC, and TJC in Part A (ITT Population)

Window Label	Target Day	Interval
Baseline	1	≤ 1
Week 16	113	[2, 225*]

Rx Day calculated relative to first dose date of study drug. For subjects randomized but not dosed, Rx Day calculated relative to Randomization.

* The minimum of upper bound and the day of the first dose date in Part B.

Table 6. Visit Windows for Analysis of PASI, Vital Signs, and Local Tolerability in Part B (ITT/Safety Population)

Window Label	Target Day	Interval
Entry of Part B	1	$\leq 1^a$
Week 22	43	[2, 64]
Week 28	85	[65, 106]
Week 34	127	[107, 148]
Week 40	169	[149, 190]
Week 46	211	[191, 232]
Week 52	253	[233, 267]
Week 56	281	[268, 295 ^b]

Rx Day calculated relative to the first dose date on or after Week 16 for PBO/RZB_75 and PBO/RZB_150 arms, and relative to the date of Week 16 visit for RZB_75/RZB_75 and RZB_150/RZB_150 arms. PASI only evaluated from Week 22 to 52. Local tolerability only evaluated from Week 22 to 40.

a. If time is collected for vital sign, restrict to records prior to the first dose of study drug in Part B.

b. The minimum of upper bound and 105 days after the last dose.

Subjects who enter the Open Label Extension Study 1311.31 will not have Week 56 evaluations.

Table 7. Visit Windows for Analysis of sPGA, PSS, DLQI, HAQ-DI, Pain VAS, Investigator's Global Assessment VAS, Patient's Global Assessment VAS, SJC, TJC, Laboratory Tests, and ECG in Part B (ITT/Safety Population)

Window Label	Target Day	Interval
Entry of Part B	1	≤ 1
Week 28	85	[2, 127]
Week 40	169	[128, 211]
Week 52	253	[212, 294 ^a]

Rx Day calculated relative to the first dose date on or after Week 16 for PBO/RZB_75 and PBO/RZB_150 arms, and relative to the date of Week 16 visit for RZB_75/RZB_75 and RZB_150/RZB_150 arms.

a. The minimum of upper bound and 105 days after the last dose.

Table 8. Visit Windows for Summary of Study Drug Injections in Part A

Window Label	Target Day	Time Window
Week 0	1	≤ 1
Week 4	29	[2, 57 ^a]

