8.0 Patient Disposition

The number of subjects for each of the following categories will be summarized, for overall and for each treatment group in the ITT population:

- Number of subjects randomized
- Number of subjects treated
- Number of subjects who completed the study
- Number of subjects who discontinued the study drug
- Number of subjects who prematurely discontinued study

In addition, the reasons for premature discontinuation will be summarized with frequencies and percentages.

In addition to patient disposition, number of screening failures and reasons for screening failure will also be summarized among all screened subjects in a subject screening status table.

The summaries will be provided for Part A and Part B.

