10.1.4 Missing Data Imputations

Missing data will be imputed using the following methods for the efficacy analyses:

- Non-Responder Imputation (NRI): The NRI analysis will categorize any subject who has missing value at a specific visit as non-responder for that visit. The only exception is when if the subject is a responder both before and after this specific visit window, then the subject will be categorized as a responder for the visit. The NRI will be the primary approach in the analysis of categorical variables. Of note, this before- and after-window imputation will utilize visits across Part A and B for the risankizumab arms.
- Last Observation Carried Forward (LOCF): The LOCF analyses will use the completed evaluation from the previous visit for efficacy measures assessed to impute missing data at later visits. For observations in RZB_75/RZB_75, and RZB_150/RZB_150 arms in Part B, LOCF is continued across Part A and Part B. LOCF will be applied to the observations in PBO/RZB_75, and PBO/RZB_150 arms within the analysis period. Baseline values will not be carried forward. LOCF will be the primary approach in the analyses of continuous variables, and the secondary approach in the analyses of categorical variables.
- As-observed: The as-observed analysis will not impute values for missing evaluations, and thus a subject who does not have an evaluation on a scheduled visit will be excluded from the as observed analysis for that visit. As-observed analysis will be the secondary approach in the analysis of continuous variables.
- Multiple Imputation (MI): The MI will be used as sensitivity approach to impute missing data in primary endpoints. The variables to be included in the imputation model are listed below. If MI is not applicable due to the nature of our data (e.g., MCMC algorithm does not converge), logistic regression or mixed effect model repeat measurement (MMRM) methods will be applied as sensitivity approach, whichever applicable.

The Multiple Imputation analysis will be carried out in three steps.

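### At the Week 28 interim, LOCF responder rates for PASI and sPGA run past Week 28, and the SAP does not limit the carry-forward to visits that were due

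*SAP*

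**What the plan says.** The interim takes place once the last patient has completed Week 28. SAP 10.1 sets a general limit and then lifts it for one group: "For this primary analysis, all endpoints will be analysed up to Week 28, with the following exception". The exception covers categorical PASI and sPGA endpoints under LOCF, which "will be analysed up to the last visit that at least one subject has observed PASI and sPGA measurements, respectively".

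SAP 10.1.4 defines the method: "The LOCF analyses will use the completed evaluation from the previous visit for efficacy measures assessed to impute missing data at later visits". It attaches no condition that the later visit was due, that its window had closed, or that the patient had left the study. The same section ranks the methods:

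- NRI is primary for categorical variables.
- For LOCF, "LOCF will be the primary approach in the analyses of continuous variables, and the secondary approach in the analyses of categorical variables".
- "As-observed analysis will be the secondary approach in the analysis of continuous variables".
- Multiple imputation is reserved for the primary endpoint.

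Other relevant text:

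- SAP 4.4 gives the report's focus: "an interim report will be prepared for the submissions analysis pertaining to Part A". Week 28 stands in for the Week 52 endpoints.
- SAP 6.0, Table 6, gives the PASI visits after Week 16: "PASI only evaluated from Week 22 to 52". Table 7 gives sPGA at Weeks 28, 40 and 52.
- SAP 5.1 uses the ITT population in Part B and leaves out only placebo patients who do not enter Part B.
- The 15 December 2017 cutoff appears in SAP 9.0 with exposure and in SAP 11.2.1 with treatment-emergent adverse events. No sentence applies it to efficacy.
- SAP 8.0 tabulates disposition, including study completers: "The summaries will be provided for Part A and Part B". SAP 9.0 counts patients dosed at each administration visit, the last being Week 40.

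**The concern.** When the last patient reaches Week 28, patients randomised earlier have reached Week 34, 40, 46 or 52. Once one patient has a score at a late visit, the exception opens a column for that visit. The LOCF rule then gives everyone not yet there a value taken from an earlier visit. A patient who missed Week 52 and a patient whose Week 52 lies months ahead are treated alike.

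Maintenance of response at Week 52 is a stated objective (Protocol 2.2, SAP 4.1), and the interim report is written for regulatory submission. A column headed Week 52 but filled partly with Week 28 to Week 46 scores could be read as evidence of maintenance. The bias has no single direction. Carry-forward cannot show a later loss of response in any arm. It also understates continuing gain in the placebo-switch arms, which started active drug only at Week 16. The primary categorical method offers no check on these columns, because NRI ends at Week 28.

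**Working it through.** **Columns affected.** From SAP Tables 6 and 7, the visits after Week 28 are Weeks 34, 40, 46 and 52 for PASI, and Weeks 40 and 52 for sPGA. Every patient still in follow-up has passed Week 28. If no earlier visit was missed, the carried scores therefore come from Weeks 28 to 46 for PASI and from Week 28 or 40 for sPGA.

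**Size.** The plan gives no figure on this point, so there is none to reproduce. The documents also give no accrual dates.

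Inputs for the base case:

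- Earliest randomisation 19 September 2016: protocol date 5 September 2016 plus the 14-day minimum between screening and Visit 2 (Protocol 6.2.1). Assumed.
- Last randomisation 2 June 2017, so that the last patient reaches Week 28 at the cutoff. Assumed.
- The 15 December 2017 cutoff governs efficacy. Assumed.
- Even accrual over the 256 days between those dates, nominal visit days, no dropout. Assumed.

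Formula: share carried forward = 1 − F(d/256). Here d is the number of days from 19 September 2016 to the latest randomisation date that reaches the visit by the cutoff, and F(t) is the share randomised by fraction t of accrual. For even accrual F(t) = t.

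| Visit (nominal day) | Latest randomisation date | d | Observed | Carried forward |
|---|---|---|---|---|
| Week 34 (239) | 21 Apr 2017 | 214 | 214/256 = 83.6% | 16.4% |
| Week 40 (281) | 10 Mar 2017 | 172 | 172/256 = 67.2% | 32.8% |
| Week 46 (323) | 27 Jan 2017 | 130 | 130/256 = 50.8% | 49.2% |
| Week 52 (365) | 16 Dec 2016 | 88 | 88/256 = 34.4% | 65.6% |

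In the base case the Week 52 column would hold about 56 × 0.344 = 19 observed patients in each risankizumab arm and 28 × 0.344 = 10 in each placebo-switch arm.

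**Other assumptions, share carried forward:**

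| Scenario | Wk 34 | Wk 40 | Wk 46 | Wk 52 |
|---|---|---|---|---|
| Front-loaded, F(t) = √t | 8.6% | 18.0% | 28.7% | 41.4% |
| Back-loaded, F(t) = t² | 30.1% | 54.9% | 74.2% | 88.2% |
| Accrual closed 5 May 2017 (228 days) | 6.1% | 24.6% | 43.0% | 61.4% |
| 28-week accrual (from 18 Nov 2016) | 21.4% | 42.9% | 64.3% | 85.7% |
| Efficacy data run 56 days past the cutoff | 0% | 10.9% | 27.3% | 43.8% |
| Same, and front-loaded | 0% | 5.6% | 14.8% | 25.0% |

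For example, the last row at Week 52 is 1 − √((88 + 56)/256) = 1 − 0.75 = 25.0%, and at Week 40 it is 1 − √(228/256) = 5.6%.

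**Shorter accrual.** With even accrual over A weeks ending 2 June 2017, the share carried forward at Week w is (w − 28)/A. If A is below 24, no patient reaches Week 52 at nominal days and that column does not arise. The Week 40 share is then 12/A, which exceeds one half for A between 12 and 24: 12/20 = 60% at A = 20. At A = 12, Week 34 is 6/12 = 50% carried forward.

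**The case against.** The best counter-argument is that a visit not yet due is not missing, so a programmer might leave such patients out. The SAP does not say so. It defines no such exclusion and keeps the ITT population in Part B. Exempting LOCF alone also fits the fill-forward reading, because NRI would score patients not yet due as non-responders; that last step is inference. The SAP does not state the carry-forward outright either, so the point rests on the rule as written.

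Several other objections stand, and they limit the point:

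- A reader might infer that nothing in the report would reveal how much was observed. That goes too far. Protocol 6.2.3.2 defines completion as reaching FU2, which is Week 52, so Part B completer counts approximate the observed number there. The dosing summary approximates Week 40. Both are inexact: scores can be missed, and patients off drug may still attend. Weeks 34 and 46 can only be bracketed by neighbouring visits.
- A reader might infer that an as-observed rate was withheld from these columns in particular. It was not: as-observed responder rates are planned at no visit. Only the NRI stop at Week 28 is specific to the interim.
- Time to loss of response (SAP 10.1.3), with Kaplan-Meier estimates and censoring at the last assessment, would show loss without carry-forward. The SAP leaves unclear whether the Week 28 limit truncates it at the interim.
- All the percentages rest on assumed accrual and on an assumed efficacy cutoff.

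**Conclusion.** The point holds and is minor. As written, the interim would report LOCF responder rates under Week 34 to Week 52 labels that include patients whose visits were not yet due, with no NRI rate beside them. The share is about 16%, 33%, 49% and 66% at the four visits in the base case, and about 25% to 88% at Week 52 across the other scenarios that produce such a column. These figures illustrate the size; they do not estimate what happened.

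Two stronger readings are tempting and unsupported. First, a reader might infer from the one-subject threshold that a late column would rest on almost nobody. The rule allows it (167 of 168 carried forward, 99.4%), but the documents give no accrual dates that would make it likely. Second, a reader might infer damage to the trial's conclusions. There is none: all patients are past Week 16 at the interim, so the Week 16 tests and alpha control are untouched, and the final Week 52 analysis is made when every visit has been due, with NRI as the primary method. LOCF is the secondary categorical method, Week 52 endpoints are descriptive (SAP 10.3), and the interim report centres on Part A and Week 28.

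**What to change.** Delete the exception in SAP 10.1, so that LOCF also stops at Week 28 in the interim. Alternatively, keep the later columns but include only subjects whose visit, with its window, was due by a stated efficacy data cutoff, apply LOCF only within that set, and show the observed number (and so the number carried forward) per arm at each visit.

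The cost is one deleted bullet, or one denominator rule and the added counts. The downside is fewer or smaller late-visit columns in the interim report.

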10.1.1 Analyses of Categorical Variables

For categorical variables, frequencies and percentages will be summarized. Treatment comparison will be conducted using a Cochran-Mantel-Haenszel (CMH) test with stratification factors as strata for the analysis. The CMH test will use weights proposed by Greenland & Robins, which is calculated as follows:

$$\hat{\delta}_{MH} = \frac{\sum_{i=1}^u w_i \cdot \hat{\delta}_i}{\sum_{i=1}^u w_i}, \text{ where}$$

$\hat{\delta}_i = \frac{x_i}{n_i} - \frac{y_i}{m_i}$ denotes the risk difference in stratum $i, i = 1, \dots, u$

$w_i = \frac{n_i \cdot m_i}{n_i + m_i}$ denotes the weight of stratum $i, i = 1, \dots, u$

x_i denotes the number of subjects with event in treatment₁ in stratum $i, i = 1, \dots, u$

y_i denotes the number of subjects with event in treatment₂ in stratum $i, i = 1, \dots, u$

n_i denotes the number of subjects on treatment₁ in stratum i, $i = 1, \dots, u$

m_i denotes the number of subjects on treatment₂ in stratum i, $i = 1, \dots, u$

The estimated variance of $\hat{\delta}_{MH}$ is calculated as:

$$\widehat{var}(\hat{\delta}_{MH}) = \frac{\sum_{i=1}^u L_i}{(\sum_{i=1}^u w_i)^2}$$

$$\text{where } L_i = \frac{x_i(n_i - x_i) m_i^3 + y_i(m_i - y_i) n_i^3}{n_i \cdot m_i \cdot (n_i + m_i)^2}, i = 1, \dots, u$$

Assuming a normal distribution of $\hat{\delta}_{MH}$, an approximate 95% CI is given as follows, where $z_{0.975}$ is the 97.5% quantile of the standard normal distribution:

$$CI = \left[\hat{\delta}_{MH} \pm z_{0.975} \cdot \sqrt{\widehat{var}(\hat{\delta}_{MH})} \right]$$

Also, the approximate p-value can be calculated using the following:

$$\text{pvalue} = 2 \cdot \Pr \left[Z > \left| \frac{\hat{\delta}_{MH}}{\sqrt{\widehat{var}(\hat{\delta}_{MH})}} \right| \right], \text{ where } Z \sim N(0, 1)$$

If there is a stratum for a treatment group that has 0 subjects in any cell in the contingency table, all cells from the stratum will be added by 0.1 in order to prevent dividing by 0 in the above equations, as suggested in Greenland & Robins.

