7.3.1 Primary endpoint analyses

The achievement of PASI 90 at Week 16 is the primary endpoint and is a binary variable with values of 0 or 1. The difference in proportion responding between the BI 655066 arm and placebo arm will be estimated and tested using the Cochran-Mantel-Haenszel risk difference estimate stratified by the randomisation factors of concomitant disease of PsA at baseline (Yes versus No) and body weight (≤ 90 kg versus >90 kg) with weights proposed by Greenland & Robins, which is calculated as follows:

$$\hat{\delta}_{MH} = \frac{\sum_{i=1}^u w_i \cdot \hat{\delta}_i}{\sum_{i=1}^u w_i}, \text{ where}$$

$$\hat{\delta}_i = \frac{x_i}{n_i} - \frac{y_i}{m_i} \text{ denotes the risk difference in stratum } i, i = 1, \dots, u$$

$$w_i = \frac{n_i \cdot m_i}{n_i + m_i} \text{ denotes the weight of stratum } i, i = 1, \dots, u$$

x_i denotes the number of patients with event in treatment₁ in stratum $i, i = 1, \dots, u$

y_i denotes the number of patients with event in treatment₂ in stratum $i, i = 1, \dots, u$

n_i denotes the number of patients on treatment₁ in stratum $i, i = 1, \dots, u$

m_i denotes the number of patients on treatment₂ in stratum $i, i = 1, \dots, u$

The estimated variance $\hat{\delta}_{MH}$ is calculated as:

$$\widehat{var}(\hat{\delta}_{MH}) = \frac{\sum_{i=1}^u L_i}{(\sum_{i=1}^u w_i)^2}$$

$$\text{where } L_i = \frac{x_i(n_i - x_i) m_i^3 + y_i(m_i - y_i) n_i^3}{n_i \cdot m_i \cdot (n_i + m_i)^2}, i = 1, \dots, u$$

Assuming a normal distribution of $\hat{\delta}_{MH}$, an approximate 95 % CI is given as follows, where $z_{0.975}$ is the 97.5% quantile of the standard normal distribution:

$$CI = \left[\hat{\delta}_{MH} \pm z_{0.975} \cdot \sqrt{\widehat{var}(\hat{\delta}_{MH})} \right]$$

Also, the approximate p-value can be calculated using the following:

$$pvalue = 2 \cdot Pr \left[Z > \left| \frac{\hat{\delta}_{MH}}{\sqrt{\widehat{var}(\hat{\delta}_{MH})}} \right| \right], \text{ where } Z \sim N(0, 1)$$

If there is a stratum for a treatment group that has 0 patients in it, the 0 count will be replaced by 0.1 in order to prevent dividing by 0 in the above equations, as suggested in Greenland & Robins. Treatment versus placebo comparisons will include both a p-value and 95% confidence interval.

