7.7 DETERMINATION OF SAMPLE SIZE

The study is powered to show a benefit of BI 655066 over placebo in terms of PASI 90 response at Week 16. Based on the outcome from the trial 1311.2, the PASI 90 response rate at Week 16 is assumed to be at least 65% in the BI 655066 arm. There is only minimal data available on placebo response in the BI 655066 program but the phase 3 results from ustekinumab and secukinumab indicate a response rate for PASI 90 of approximately 5% in the placebo arm. With 2-sided significance level 5%, based on these assumptions (65% vs 5% PASI 90 response rates), 17 patients in the BI 655066 arm and 17 in the placebo arm will provide 95% power for each comparison and an overall power of at least 90%.

For the Japanese submission, the safety data of at least 100 Japanese patients exposed to BI 655066 at the registered dose(s) for 1 year or more is necessary for long team safety assessment as a result of the PMDA consultation meeting in 2015. This study will enrol a total of 168 patients, with 56 patients in each of the two BI 655066 arms and 56 patients in the placebo arm. It is expected that at least 68 patients exposed to BI 655066 75 mg and 68

Proprietary confidential information © 2017 Boehringer Ingelheim International GmbH or one or more of its affiliated companies

patients exposed to BI 655066 150 mg will reach at least 1 year exposure to BI 655066 in this clinical trial or in the following extension study. Other global phase III trials where Japanese patients are to be enrolled will make up for the remaining safety data requirements.

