10.3 Secondary Efficacy Analyses

Secondary endpoints will be analysed in the ITT Population. The same methods as discussed for the primary analyses will be used to analyze all binary secondary endpoint at Week 16.

Secondary endpoints for Week 52 will be summarized descriptively.

Secondary Efficacy Endpoints are:

- Achievement of PASI 90 at Week 52
- Achievement of an sPGA score of clear or almost clear at Week 16
- Achievement of an sPGA score of clear or almost clear at Week 52
- Achievement of $\geq 75\%$ reduction from baseline PASI score (PASI 75) at Week 16
- Achievement of PASI 75 at Week 52
- Achievement of 100% reduction from baseline PASI score (PASI 100) at Week 16
- Achievement of PASI 100 at Week 52

- Achievement of an American College of Rheumatology (ACR) 20 response at Week 16, among subjects with confirmed diagnosis of PsA using CASPAR criteria and with baseline total TJC and SJC counts ≥ 3 at selected study sites
- Achievement of an ACR 20 at Week 52, among subjects with confirmed diagnosis of PsA using CASPAR criteria and with baseline total TJC and SJC counts ≥ 3 at selected study sites

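### SAP 10.1.1 and protocol 7.3.1 give different zero-count corrections for the same primary estimator, and either one, read literally, pads the empty strata in ACR 20 (minor)

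*SAP*

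**What the plan says.** Both documents print the same stratified risk difference with Greenland and Robins weights, the same variance, and a p-value from the estimate divided by its standard error. They differ in what happens at a zero count.

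- Protocol 7.3.1: "If there is a stratum for a treatment group that has 0 patients in it, the 0 count will be replaced by 0.1". The trigger is an arm with no patients in a stratum.
- SAP 10.1.1: the trigger is a zero in any cell of a stratum's contingency table, and then "all cells from the stratum will be added by 0.1 in order to prevent dividing by 0 in the above equations". A stratum with patients in both arms but no placebo responders qualifies.

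Both attribute their rule to the same source. SAP 14.1, the section for changes from the protocol, shows no entry in the text available.

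SAP 10.3 carries the method over: "The same methods as discussed for the primary analyses will be used to analyze all binary secondary endpoint at Week 16". That includes ACR 20, which SAP 10.3 restricts to patients with CASPAR-confirmed PsA and joint counts of at least 3 at selected sites.

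**The concern.** The SAP gives avoidance of division by zero as its reason, but zero responders or zero non-responders do not make a divisor zero in the estimate or its variance. With placebo response near 5% spread over four strata, a zero cell is the usual case. The wider rule would therefore be the normal path for the primary analysis, and the reported risk difference and CI would not be the ones the protocol defines. All three arms are affected together: the placebo group is shared, so one stratum without placebo responders triggers the rule in both dose comparisons.

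In ACR 20 the strata for patients without PsA should contain nobody. If they are kept and padded, they enter the weighted average with a difference of zero.

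**Working it through.** **Inputs.** Protocol 7.7: "With 2-sided significance level 5" per cent; "the PASI 90 response rate at Week 16 is assumed to be at least 65% in the BI 655066 arm"; earlier trials "indicate a response rate for PASI 90 of approximately 5% in the placebo arm"; 56 patients per arm. There are four strata (PsA yes/no by weight at 90 kg). The documents give no stratum sizes, ACR 20 subset size or ACR 20 rates, so these are assumed below.

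**The plan's own figure.** Protocol 7.7 claims 95% power per comparison, and 90% or more overall, from "17 patients in the BI 655066 arm and 17 in the placebo arm". The usual two-proportion formula gives

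n = [1.960 × √(2 × 0.35 × 0.65) + 1.645 × √(0.65 × 0.35 + 0.05 × 0.95)]² / 0.60² = 13.3, or 14 per arm.

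The continuity correction gives (13.26/4) × [1 + √(1 + 4/(13.26 × 0.60))]² = 16.4, or 17. The figure is reproduced. Fisher exact power at 17 per arm is 96.7%; at 56 per arm power exceeds 99.99%.

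**Is there a zero divisor?** The divisors in the estimate and variance are n, m, n + m and the sum of the weights, which are all arm sizes. Take 6/9 versus 0/9:

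- w = 81/18 = 4.5
- L = (6 × 3 × 9³ + 0)/(9 × 9 × 18²) = 0.5

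Both are finite. The p-value also divides by the standard error, which is 0 only if every stratum in both arms has 0% or 100% response.

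**How often the rule fires.** For a comparison with stratum sizes n_i in each arm,

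P(fires) = 1 − Π (1 − 0.65^n_i − 0.35^n_i)(1 − 0.95^n_i − 0.05^n_i).

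A stratum with one patient per arm always has a zero cell.

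| Stratum sizes per arm (assumed) | P(fires) |
|---|---|
| 14/14/14/14 | 93.2% |
| 22/6/22/6 | 97.3% |
| 31/8/13/4 | 98.1% |
| 36/9/9/2 | 99.5% |
| 45/5/5/1 | 100% |

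Across these splits a 2% placebo rate gives 99.6 to 100%, and a 10% rate gives 65 to 100%. With only two filled strata and 5% placebo response it is 42 to 62%.

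**How far it moves the estimate.** With equal arms in a stratum, w × difference = (x − y)/2, and adding 0.1 to every cell leaves this unchanged. Each corrected stratum adds 0.1 to the sum of weights, which is 28 at 56 per arm. With k corrected strata the estimate is multiplied by 28/(28 + 0.1k). A 60-point difference becomes 59.8, 59.6, 59.4 or 59.2 for k = 1 to 4.

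Worked table: strata 36/9/9/2, active responders 23, 6, 6, 1, placebo responders 3, 0, 0, 0.

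- No correction: 16.5/28 = 0.589, SE 0.0704, 95% CI 0.451 to 0.727, z = 8.37.
- SAP rule (k = 3): 16.5/28.3 = 0.583, SE 0.0707, 95% CI 0.445 to 0.722, z = 8.25.

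Over 200,000 simulated trials per split, the mean went from 0.600 to between 0.594 and 0.596, and the mean SE from 0.0674 to about 0.0677. With randomly unequal arms, 99.99% of the trials in which the rule fired moved toward zero.

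**ACR 20.** A stratum empty in both arms and padded under the SAP rule has 0.2 patients per arm, weight 0.2 × 0.2/0.4 = 0.1 and difference 0. Under the protocol's wording it has 0.1 per arm, weight 0.1 × 0.1/0.2 = 0.05 and difference 0. With 5 per arm the real weight is about 2.5, so the two no-PsA strata alone multiply the SAP estimate by about 2.5/2.7 = 0.93; with 10 per arm, by about 5/5.2 = 0.96. Simulated means at an assumed 60% versus 20%, SAP rule throughout:

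| Per arm (assumed) | Doubly empty strata dropped | Doubly empty strata padded |
|---|---|---|
| 5 | about 37.5 points | about 34.4 points |
| 10 | about 39.1 points | about 37.6 points |

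**The case against.** The strongest reply is that the SAP rule does some good. In simulations with 5% response in both arms, the printed Wald test rejects in about 5.9% of trials without the correction and 3.6 to 3.9% with it (5.8 to 6.3% and 3.4 to 3.6% for the fixed splits above). At 65% versus 5%, CI coverage is about 94.2% with the rule and 93.5% without. In an ACR 20 subset of 5 per arm, coverage is 91% with the rule and 82% with the protocol's trigger and weight strata only. All of this stands, and it must be disclosed with any change.

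It is also true that zero counts can stop the p-value. The total variance is 0 in about 0.3% of primary trials at 5% versus 5%, and this never occurred in the simulations at 65% versus 5%. In ACR 20 with 5 per arm it occurs in about 5% of trials at 60% versus 20% and 13% at 20% versus 20%. A reader might infer that the SAP's reason is wholly empty; the p-value formula does not support that. The exception calls for a fallback on the total variance and does not need a trigger in each stratum.

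A reader might also infer that the SAP introduced the padding of empty strata. It did not, since the protocol's wording pads them too, at half the weight. The padding also depends on a literal reading in which a stratum with no patients counts as having a contingency table.

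Finally, a reader might infer that a CMH chi-square test should supply the p-value, because SAP 10.1.1 speaks of a CMH test. That section says the test uses the Greenland and Robins weights and prints the Wald p-value, as the protocol does. Replacing it would be a preference and would depart from both documents.

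**Conclusion.** The conflict is real and minor. The two documents specify different corrections for one primary estimator. At the plan's own rates with four filled strata, the SAP's version applies in about 93 to 100% of comparisons. It costs about half a percentage point on a 60-point difference, against a CI of roughly 14 points on each side.

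The stronger reading, that the rule endangers the primary result, is not supported. The shift is conservative, and power at 56 per arm is about 100% either way.

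The ACR 20 effect is larger, about 3 points at 5 per arm and 1.5 at 10. It holds only if empty strata are padded, and the subset size and response rates are assumptions. ACR 20 also lies outside the testing order in SAP 10.4.

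The firing rate depends on the placebo rate and on how many strata are filled. The source that both documents cite was not available, so neither attribution was checked.

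**What to change.** 1. State in SAP 10.1.1 that strata with no patients in either arm are dropped, and in SAP 10.3 that ACR 20 is stratified by body weight only. This removes the artificial pull toward zero whichever correction is kept.
2. For the primary estimate, do one of the following:
   - limit the SAP correction to strata where an arm has no patients, as in the protocol, and pre-specify a fallback for a total variance of 0; or
   - keep the wider rule, enter it in SAP 14.1 as a change from the protocol, and replace the division-by-zero reason with the actual one, such as better error control and coverage with sparse strata.

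The cost is SAP wording and minor programming. The first option makes the printed test slightly liberal (about 5.9% instead of 3.6 to 3.9% at a 5% null). It also lowers CI coverage, slightly for the primary endpoint and markedly in a very small ACR 20 subset. The second option has neither drawback, but the reported estimate stays about half a point below the protocol's. The p-value formula printed in both documents should stay.
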